16.2 Ora Calibra Drop Comfort Assessment

Ora Calibra® Drop Comfort Scale will be used at Visits 2, 4 and 5 to assess drop comfort for each eye separately upon instillation, and at 1 and 2 minutes post-instillation. The scale ranges from 0 to 10, with 0 indicating very comfortable and 10 indicating very uncomfortable. The scale will be summarized using continuous descriptive statistics by visit, time point and eye (study eye and fellow eye) for each treatment group.

Ora Calibra® Drop Comfort Questionnaire will be used to assess drop comfort 3 minutes post-instillation. Subjects will be asked to choose three words (among 12) that best describe how the eye drops feel in both eyes. The positive responses are comfortable, cool, refreshing, smooth, and soothing. The negative responses include burning, irritating, filmy, gritty, sticky, stinging, and thick. Subjects may also select “other” and write in a response of their choosing, which may be either a positive or a negative response. The results will be summarized for each response individually and for positive and negative responses using counts and percentages for each treatment group at each visit for each eye (study eye and fellow eye). Percentages will be based on the number of subjects in each treatment group with responses. A subject listing of the drop comfort assessment parameters will also be produced.

16.3 Best-corrected Visual Acuity (BCVA)

The visual acuity procedure will be performed at each visit pre-CAE®. The logarithm of the minimum angle of resolution (logMAR) VA must be assessed using an ETDRS chart. The procedure used will be

consistent with the recommendations provided for using the ETDRS eye chart. Visual Acuity should be evaluated at the beginning of each visit in the study (i.e., prior to slit-lamp examination). Subjects should use their most recent correction to attain their BCVA.

The observed and change from baseline visual acuity will be summarized for each eye (study eye and fellow eye) using continuous descriptive statistics by visit for each treatment group. A subject listing of visual acuity will also be produced.

16.4 Slit-lamp Biomicroscopy

A slit-lamp biomicroscopy examination of the cornea, conjunctiva, anterior chamber, iris, lens, and eyelid will be performed at each visit, and potentially at an Early Termination Visit. Both pre- and post-CAE® examinations will be made at Visits 1 and 5. The results will be graded as normal, Abnormal Not Clinically Significant (NCS) or Abnormal Clinically Significant (CS). Abnormal findings will be described.

The results will be summarized using counts and percentages for each treatment group at each visit for each eye (study eye and fellow eye). Percentages will be based on the number of subjects in each treatment group with responses. Shift tables for the slit-lamp biomicroscopy parameters will also be provided comparing each follow-up visit to Visit 1, Pre-CAE. A subject listing of the slit-lamp biomicroscopy parameters will also be produced.

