10.3.1.2 Visit 2: Baseline & Randomization (Day 1)

- Study drug collection
- Medical/medication history update
- Inclusion and exclusion criteria
- Patient symptoms using the Visual Analog Scale
- Ocular Discomfort Score
- OSDI
- SANDE
- BCVA with manifest refraction
- Vital signs
- Bulbar conjunctival hyperemia scores (Ora Calibra® Conjunctival Redness for Dry Eye Scale)
- Slit-lamp biomicroscopy
- Tear Collection (selected sites)

- Oculus Keratograph 5® procedures: TBUT and tear meniscus height (selected sites)
- TFBUT
- Sodium fluorescein corneal staining, using the Oxford scale and Ora Calibra® scales
- Lissamine green conjunctival staining, using the Oxford scale
- 15+ minute wait from end of Lissamine staining to start of Schirmer's Test
- Schirmer without anesthesia
- Intraocular pressure (IOP)
- Randomization
- Blood sample collection for systemic pharmacokinetics (in selected Stage 1 patients)
- Administer AXR-159 Ophthalmic Solution or vehicle in both eyes (must NOT be done before blood and tear sample collection)
- Ora Calibra® Drop Comfort Assessment
- Collect and dispense study drug
- Adverse event query

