8.3 Definition of Baseline

Baseline measures are defined as the last measure prior to the initiation of study treatment, usually at Day 1. If a measure is taken both pre-CAE® and post-CAE®, the baseline will be the last time point matched value prior to the initiation of study treatment. For post-CAE® measures, this will be at Day -14. For changes from pre-CAE® to post-CAE® post first treatment, the change from pre-CAE® to post-CAE® at Day -14 will be considered the baseline value.

Changes from baseline will be calculated as visit minus baseline and summarized by treatment and visit as described above. Treatment comparisons between an active treatment and vehicle will be calculated as active minus vehicle.

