8.4 Data Analysis Conventions

All data analysis will be performed by Statistics & Data Corporation (SDC) after the study is completed and the database has been locked and released for unmasking. Statistical programming and analyses will be performed using SAS® Version 9.4 or higher. Output will be provided in rich text format (RTF) for tables and portable document format (PDF) for tables, listings, and figures using landscape orientation. All study data will be listed by subject, treatment, and visit (as applicable) based on all randomized subjects unless otherwise specified.

Summaries for continuous and ordinal variables will include the number of observations (n), arithmetic mean, standard deviation (SD), median, minimum, and maximum). Minima and maxima will be reported with the same precision as the raw values; means and medians will be presented to one additional decimal place than reported in the raw values. SDs will be presented to two additional decimal places than reported in the raw values. Summaries for discrete variables will include frequency counts and percentages. All percentages will be rounded to one decimal place (i.e., XX.X%). Differences between active treatment groups and vehicle will be calculated as Active minus Vehicle and change from baseline will be calculated as follow-up visit minus baseline. The baseline measure will be defined as the last non-missing measure prior to initiation of investigational treatment.

Statistical comparisons between each AXR-159 Ophthalmic Solution group will be to the vehicle group at matched dosing frequency (TID or BID). AXR-159 Ophthalmic Solution plus Artificial Tear group will be compared to both AXR-159 Ophthalmic Solution and to the vehicle group at matched dosing frequency.

A final database lock will occur at the completion of Stage 2 and the safety, tolerability, and efficacy data from both Stage 1 and 2 will be analyzed separately and in a combined fashion to fully leverage the advantage of this two-stage study design.

All statistical tests will be two-sided with a significance level of 0.05 ($\alpha = 0.05$) unless otherwise specified. Confidence intervals (CI) for differences between treatment groups will be two-sided at 95% confidence. All p-values will be rounded to four decimal places; p-values less than 0.0001 will be presented as “<0.0001”; p-values greater than 0.9999 will be presented as “>0.9999”.

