16.5 Intraocular Pressure (IOP)

IOP will be measured in each eye by contact tonometry by the examiner and the results will be recorded in mmHg at all scheduled visits, and potentially at an Early Termination Visit. Assessments at Visits 1 and 5 will be post-CAE®. A single measurement is made to obtain a determination of IOP. The same tonometer employing the investigator's standard technique will be used throughout the study. In addition, all reasonable efforts will be made to have the same examiner obtain all IOP measurements for a given subject.

The IOP values and changes from baseline for each eye (study eye and fellow eye) will be summarized using continuous descriptive statistics by visit and eye for each treatment group and for all actively treated subjects. A subject listing of IOP will also be produced.

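### Slit-lamp shift tables in SAP 16.4 take Visit 1 pre-CAE as reference instead of the Day 1 baseline, so changes during the vehicle run-in are mixed into the within-arm on-treatment shifts

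*SAP*

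**What the plan says.** SAP 16.4 plans slit-lamp counts and percentages by visit and eye, a subject listing, and shift tables "comparing each follow-up visit to Visit 1, Pre-CAE". It also states: "Both pre- and post-CAE® examinations will be made at Visits 1 and 5". It does not say which of the two Visit 5 exams enters the shift table.

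The general rule is in SAP 8.3: "Baseline measures are defined as the last measure prior to the initiation of study treatment, usually at Day 1". For a measure taken both before and after the chamber, "the baseline will be the last time point matched value prior to the initiation of study treatment", and then: "For post-CAE® measures, this will be at Day -14". Protocol 12.4.1 has the same rule. SAP 8.4 restates it more briefly: "The baseline measure will be defined as the last non-missing measure prior to initiation of investigational treatment".

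The Day 1 exam exists. Protocol 10.3.1.2 lists "Slit-lamp biomicroscopy" among the Visit 2 procedures, before randomisation, and the visit schedules in both documents agree.

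Protocol Table 4-1 names shift tables for safety variables, including biomicroscopy, among the endpoints for the primary objective. SAP 16.4 gives no reason for its different reference, and SAP 18 declares no departures from the protocol's analyses.

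**The concern.** Between Visit 1 pre-CAE and Day 1 every patient goes through a 90-minute chamber exposure and about two weeks of vehicle drops. A shift table anchored before that period and read after randomisation adds two things together: what happened in run-in and what happened on assigned treatment. A reader of the table will take the sum as the second.

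This has some practical weight. The protocol describes the trial as the first use of this compound as an eye drop in humans, so safety findings within each arm will be read directly. SAP section 20 puts tables marked Stage 1 into the interim analysis, and the Stage 1 slit-lamp shift table (14.3.5.2.1) is one of them. At that interim, dose groups may be ended for safety or tolerability. No numerical rule is tied to the table.

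**Working it through.** No sample size, power or rate enters this point, so the check sets the time points against the rules.

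**Reference by follow-up exam**

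| Follow-up exam | Reference under SAP 16.4 | Reference under SAP 8.3 | Agree? |
|---|---|---|---|
| Visit 3 (non-CAE) | Visit 1 pre-CAE | Visit 2, Day 1 | No |
| Visit 4 (non-CAE) | Visit 1 pre-CAE | Visit 2, Day 1 | No |
| Visit 5 pre-CAE | Visit 1 pre-CAE | Visit 2, Day 1; on a strictly literal match, Visit 1 pre-CAE | Arguable |
| Visit 5 post-CAE, if tabulated | Visit 1 pre-CAE | Visit 1 post-CAE | No |

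The third row is arguable because the SAP schedule labels Visit 2 as non-CAE, so Visit 1 holds the only earlier exam that carries the pre-CAE label.

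**Effect on the counts.** Write N for normal and A for abnormal, in the order Visit 1 pre-CAE, Visit 2, follow-up.

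| Pattern | Shift shown under 16.4 | Shift from Day 1 |
|---|---|---|
| N, N, A | N to A | N to A |
| N, A, A | N to A | none (A to A) |
| A, N, A | none (A to A) | N to A |
| A, N, N | A to N | none (N to N) |
| N, A, N | none (N to N) | A to N |

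For shifts from normal to abnormal:

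- count under 16.4 = (N,N,A) + (N,A,A)
- count from Day 1 = (N,N,A) + (A,N,A)
- difference = (N,A,A) − (A,N,A)

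The difference can have either sign. It is zero only if findings that arise in run-in and persist happen to equal in number those that clear in run-in and recur. The documents give neither frequency.

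**Between arms.** The Visit 1 and Visit 2 exams both come before randomisation at the end of Visit 2. Either reference is therefore a pre-randomisation variable, balanced between arms in expectation, and the choice creates no systematic difference between them.

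**The case against.** The best defence is that 16.4 names its comparator outright, and a specific section may depart from a general convention. Visit 1 pre-CAE is the only exam before any study drop, and SAP 16.1 counts vehicle given at any stage as study drug. A reference before any exposure would be a coherent safety choice. But 16.4 does not invoke it, SAP 12.1 and 12.2 start compliance and exposure at Visit 2, and 8.3 itself places the start of study treatment at Day 1 in the usual case. Ophthalmoscopy shifts also use Visit 1, but no Visit 2 ophthalmoscopy is scheduled and SAP 16.6 expressly calls Visit 1 the baseline. That reason is not available for slit-lamp.

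It can also be said that run-in changes are visible elsewhere: 16.4 gives counts at every visit, Visit 2 included, and a listing. This stands in part. Counts by visit do not show which eyes changed; the listing does, patient by patient. Adverse event counts come from a separate source and do not depend on the shift reference.

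Three stronger readings are tempting, and the documents do not support them.

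- *That chamber effects are shown as treatment shifts.* A same-day chamber effect enters only if the Visit 5 post-CAE exam is tabulated against Visit 1 pre-CAE. The wording of 16.4 allows this but does not state it. The Visit 1 chamber exposure would have to leave a finding lasting from Day -14 to Day 15, about four weeks, to reach Visit 3, and nothing in the documents suggests that.
- *That shift counts are inflated.* The difference above has no fixed sign. Entry also requires corneal staining and conjunctival redness at Visits 1 and 2 in at least one eye, so many eyes may already be graded abnormal at Visit 1.
- *That IOP change has the same fault.* SAP 16.5 says of IOP: "Assessments at Visits 1 and 5 will be post-CAE". Under 8.3 a post-CAE measure is referred to Day -14, which matches Visit 5 with Visit 1. A mismatch arises only if 8.4 is read alone, or if the matching in 8.3 is confined to measures taken both before and after the chamber, which IOP is not. That is an ambiguity of wording, not an error.

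**Conclusion.** The slit-lamp point holds. For Visits 3 and 4, SAP 16.4 departs from the SAP's own baseline although the Day 1 exam is collected, and it does so without a reason or a declared change. For Visit 5 pre-CAE the departure is arguable. The consequence is confined to descriptive within-arm safety tables, where run-in changes are mixed with on-treatment changes in both directions. The randomised comparison is unaffected on average, and no test or decision rule depends on the table. No size can be given, because the documents contain no rate of slit-lamp change over the run-in. The conclusion rests on taking study treatment to begin at Day 1, as 8.3 indicates. The impact is low, and the correction costs almost nothing.

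**What to change.** In SAP 16.4, name the shift reference by time point: Visit 2 (Day 1) for Visits 3, 4 and 5 pre-CAE, and Visit 1 post-CAE for Visit 5 post-CAE if that exam is tabulated. State whether it is. A shift from Visit 1 pre-CAE may be kept as a supplementary table, labelled as covering run-in and treatment together. At most, SAP 16.5 could add a sentence confirming that the Day -14 post-CAE baseline in 8.3 applies to Visit 5 IOP.

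The cost is a few sentences in the SAP and a changed reference visit in the programs for Tables 14.3.5.2.1 to 14.3.5.2.3. All the exams are already scheduled, so no procedure or data collection changes.

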16.5 Intraocular Pressure (IOP)

IOP will be measured in each eye by contact tonometry by the examiner and the results will be recorded in mmHg at all scheduled visits, and potentially at an Early Termination Visit. Assessments at Visits 1 and 5 will be post-CAE®. A single measurement is made to obtain a determination of IOP. The same tonometer employing the investigator's standard technique will be used throughout the study. In addition, all reasonable efforts will be made to have the same examiner obtain all IOP measurements for a given subject.

The IOP values and changes from baseline for each eye (study eye and fellow eye) will be summarized using continuous descriptive statistics by visit and eye for each treatment group and for all actively treated subjects. A subject listing of IOP will also be produced.

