4 STUDY OBJECTIVES

TABLE 4-1 TABLE OF OBJECTIVES, ENDPOINT, AND ENDPOINT JUSTIFICATION

OBJECTIVES	ENDPOINTS	JUSTIFICATION FOR ENDPOINTS
Primary		
Stage 1: To evaluate the safety, tolerability, and exploratory pharmacodynamics of up to 2 different concentrations of AXR-159 Ophthalmic Solution (30 mg/mL or 50 mg/mL) dosed three-times daily (TID) or twice-daily (BID) for up to 12 weeks compared to its vehicle in patients with Dry Eye Disease (DED).	
Adverse Events:
 
Incidence rates of each treatment-emergent adverse event summarized by primary system organ class and preferred term.Tables for all treatment-emergent adverse events regardless of causality.Tables for all treatment-emergent adverse events considered to be treatment-related.Shift tables for safety variables (e.g., IOP, biomicroscopy, and ophthalmoscopy). 
Signal of Efficacy:
 
Change from Baseline in inferior corneal staining score in the study eyeChange from Baseline in total corneal staining score in the study eyeChange from Baseline in eye dryness measured using a visual analogue scale (VAS)Change from Baseline in Total Ocular Surface Disease Index (OSDI) score	
The endpoints for safety and tolerability are all commonly used in drug trials.
 
The efficacy endpoints match those captured in the Xiidra clinical development program and are listed on the U.S. Food & Drug Administration webpage (https://www.accessdata.fda.gov/drugsatfda_docs/nda/2016/208073Orig1s000TOC.cfm).

Stage 2: To evaluate the safety, tolerability, and pharmacodynamics of up to 3 different concentrations of	See Above for Stage 1	See Above for Stage 1

OBJECTIVES	ENDPOINTS	JUSTIFICATION FOR ENDPOINTS
AXR-159 Ophthalmic Solution (3 mg/mL, 30 mg/mL or 50 mg/mL) dosed three-times daily (TID) or twice-daily (BID) for up to 12 weeks compared to its vehicle in patients with Dry Eye Disease (DED).		
Secondary		

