SDC	Statistics and Data Corporation, Incorporated
SOC	System Organ Class

TEAE	Treatment-Emergent Adverse Event
TE-SAE	Treatment-Emergent Serious Adverse Event
TFBUT	Tear Film Break-Up Time
TID	Ter in die (three times daily)
VA	Visual Acuity
VAS	Visual Analog Scale
WHO DDE	World Health Organization Drug Dictionary Enhanced

1. Introduction

The purpose of this statistical analysis plan (SAP) is to describe the planned analyses and reporting for protocol AXR201701, version 1 dated 17Feb2018.

This SAP is being written with due consideration of the recommendations outlined in the most recent International Conference on Harmonization (ICH) E9 Guideline entitled Guidance for Industry: Statistical Principles for Clinical Trials and the most recent ICH E3 Guideline, entitled Guidance for Industry: Structure and Content of Clinical Study Reports.

This SAP describes the data that will be analyzed and the subject characteristics, efficacy, and safety assessments that will be evaluated. This SAP provides details of the specific statistical methods that will be used. The statistical analysis methods presented in this document will supersede the statistical analysis methods described in the clinical protocol. If additional analyses are required to supplement the planned analyses described in this SAP they may be completed and will be identified in the CSR.

2. Study Objectives

The primary objectives for Stage 1 are to evaluate the safety, tolerability, and exploratory pharmacodynamics of up to 2 different concentrations of AXR-159 Ophthalmic Solution (30 mg/mL or 50 mg/mL) dosed three-times daily (TID) or twice-daily (BID) for up to 12 weeks compared to its vehicle in patients with Dry Eye Disease (DED). The primary objectives for Stage 2 are to evaluate the safety, tolerability, and pharmacodynamics of up to 3 different concentrations of AXR-159 Ophthalmic Solution (3 mg/mL, 30 mg/mL or 50 mg/mL) dosed TID or BID for up to 12 weeks compared to its vehicle in patients with DED.

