16.8 Vital Signs

Each subject will have vital signs assessments (resting blood pressure and pulse) conducted at Visits 1, 2, and 5. Vital signs are to be conducted by a qualified staff member who may be any of the following: a board-certified investigator or sub-investigator, nurse practitioner, registered nurse, or physician assistant.

Systolic and diastolic blood pressure should be measured in the same arm each time using a sphygmomanometer with the subjects who have been in a resting state (seated upright) at least 5 minutes. Blood pressure will be recorded in mmHg.

Pulse will be measured with the subjects who have been in a resting state (seated) for at least 5 minutes. Pulse will be counted for 30 seconds and multiplied by 2, and recorded in beats per minute (bpm).

The vital signs and changes from baseline will be summarized using continuous descriptive statistics by visit for each treatment group and for all actively treated subjects. A subject listing of vital signs will also be produced.

Vital signs will also be presented categorically for the number of subjects with low, normal, or high values as defined by the table below:

Vital Signs	Low	Normal	High
Systolic Blood Pressure (mmHg)	<90	90-180	>180

Vital Signs	Low	Normal	High
Diastolic Blood Pressure (mmHg)	<50	50-100	>100
Pulse Rate (bpm)	<50	50-110	>110

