16.10 Urine Pregnancy Test

A urine pregnancy test will be conducted for females of childbearing potential at Visit 1 (Day -14 ± 2), Visit 5 (Day 85 ± 2), and may be conducted at an Unscheduled Visit. A listing of urine pregnancy test results will be generated.

17. Interim Analyses

An interim analysis will be performed when the last enrolled patient in Stage 1 completes Month 3 of the Expansion Cohort. There is no plan to stop the study for efficacy on the basis of the interim analysis. However, termination in individual dose groups due to safety, tolerability and/or futility may occur. Statistical significance will not be declared at the time of the interim analysis.

Given the exploratory nature of the study no Type I error adjustments will be made for the interim analysis including the Stage 1 data only.

18. Changes from Protocol-Stated Analyses

There are no changes from the protocol-stated analyses.

19. Revision History

The following revisions were made to SAP Version 2.0.

SAP Section	Revision	Rationale
12.1	Revised compliance calculation to use date of completion/discontinuation rather than date of last in-office instillation	Conservative estimation of compliance for discontinued subjects

12.2	Revised exposure calculation to use date of completion/discontinuation rather than date of last in-office instillation	Conservative estimation of exposure for discontinued subjects
13.1.1	Revised specification of random number seeds for MCMC	Consistency with 13.1.2
13.1.3, 13.1.4, 13.1.5	Revised specification of random number seeds for MCMC	Correction of seed specification

20. Tables

Tables that will be included in the topline delivery are shown in boldface font. Tables that will be included in the interim analysis are qualified as “Stage 1”.

Table Number	Title	Population
TABLE 14.1.1.1	SUBJECT DISPOSITION – STAGE 1	ALL RANDOMIZED SUBJECTS
TABLE 14.1.1.2	SUBJECT DISPOSITION – STAGE 2	ALL RANDOMIZED SUBJECTS
TABLE 14.1.1.3	SUBJECT DISPOSITION – COMBINED STAGE 1 AND STAGE 2	ALL RANDOMIZED SUBJECTS
TABLE 14.1.2.1.1	DEMOGRAPHICS – STAGE 1	MITT POPULATION
TABLE 14.1.2.1.2	DEMOGRAPHICS – STAGE 1	MITT2 POPULATION
TABLE 14.1.2.1.3	DEMOGRAPHICS – STAGE 1	SAFETY POPULATION
TABLE 14.1.2.2.1	DEMOGRAPHICS – STAGE 2	MITT POPULATION
TABLE 14.1.2.2.2	DEMOGRAPHICS – STAGE 2	MITT2 POPULATION
TABLE 14.1.2.2.3	DEMOGRAPHICS – STAGE 2	SAFETY POPULATION
TABLE 14.1.2.3.1	DEMOGRAPHICS – COMBINED STAGE 1 AND STAGE 2	MITT POPULATION

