TABLE 14.3.2.3	ORA CALIBRA® DROP COMFORT SCALE – COMBINED STAGE 1 AND STAGE 2	SAFETY POPULATION
TABLE 14.3.3.1	ORA CALIBRA® DROP COMFORT QUESTIONNAIRE – STAGE 1	SAFETY POPULATION
TABLE 14.3.3.2	ORA CALIBRA® DROP COMFORT QUESTIONNAIRE – STAGE 2	SAFETY POPULATION
TABLE 14.3.3.3	ORA CALIBRA® DROP COMFORT QUESTIONNAIRE – COMBINED STAGE 1 AND STAGE 2	SAFETY POPULATION
TABLE 14.3.4.1	BEST-CORRECTED VISUAL ACUITY (BCVA; LOGMAR) – STAGE 1	SAFETY POPULATION
TABLE 14.3.4.2	BEST-CORRECTED VISUAL ACUITY (BCVA; LOGMAR) – STAGE 2	SAFETY POPULATION
TABLE 14.3.4.3	BEST-CORRECTED VISUAL ACUITY (BCVA; LOGMAR) – COMBINED STAGE 1 AND STAGE 2	SAFETY POPULATION
TABLE 14.3.5.1.1	SLIT-LAMP BIOMICROSCOPY – STAGE 1	SAFETY POPULATION
TABLE 14.3.5.1.2	SLIT-LAMP BIOMICROSCOPY – STAGE 2	SAFETY POPULATION
TABLE 14.3.5.1.3	SLIT-LAMP BIOMICROSCOPY – COMBINED STAGE 1 AND STAGE 2	SAFETY POPULATION

Table Number	Title	Population
TABLE 14.3.5.2.1	SHIFT IN SLIT-LAMP BIOMICROSCOPY – STAGE 1	SAFETY POPULATION
TABLE 14.3.5.2.2	SHIFT IN SLIT-LAMP BIOMICROSCOPY – STAGE 2	SAFETY POPULATION
TABLE 14.3.5.2.3	SHIFT IN SLIT-LAMP BIOMICROSCOPY – COMBINED STAGE 1 AND STAGE 2	SAFETY POPULATION
TABLE 14.3.6.1	INTRAOCULAR PRESSURE (IOP; MMHG) – STAGE 1	SAFETY POPULATION
TABLE 14.3.6.2	INTRAOCULAR PRESSURE (IOP; MMHG) – STAGE 2	SAFETY POPULATION
TABLE 14.3.6.3	INTRAOCULAR PRESSURE (IOP; MMHG) – COMBINED STAGE 1 AND STAGE 2	SAFETY POPULATION
TABLE 14.3.7.1.1	OPHTHALMOSCOPY – STAGE 1	SAFETY POPULATION
TABLE 14.3.7.1.2	OPHTHALMOSCOPY – STAGE 2	SAFETY POPULATION
TABLE 14.3.7.1.3	OPHTHALMOSCOPY – COMBINED STAGE 1 AND STAGE 2	SAFETY POPULATION
TABLE 14.3.7.2.1	SHIFT IN OPHTHALMOSCOPY – STAGE 1	SAFETY POPULATION
TABLE 14.3.7.2.2	SHIFT IN OPHTHALMOSCOPY – STAGE 2	SAFETY POPULATION
TABLE 14.3.7.2.3	SHIFT IN OPHTHALMOSCOPY – COMBINED STAGE 1 AND STAGE 2	SAFETY POPULATION
TABLE 14.3.8.1	VITAL SIGNS – STAGE 1	SAFETY POPULATION
TABLE 14.3.8.2	VITAL SIGNS – STAGE 2	SAFETY POPULATION
TABLE 14.3.8.3	VITAL SIGNS – COMBINED STAGE 1 AND STAGE 2	SAFETY POPULATION
TABLE 14.3.9.1	LABORATORY TESTS – STAGE 1	SAFETY POPULATION
TABLE 14.3.9.2	LABORATORY TESTS – STAGE 2	SAFETY POPULATION
TABLE 14.3.9.3	LABORATORY TESTS – COMBINED STAGE 1 AND STAGE 2	SAFETY POPULATION
TABLE 14.3.10.1	COMPLIANCE WITH STUDY DRUG – STAGE 1	SAFETY POPULATION
TABLE 14.3.10.2	COMPLIANCE WITH STUDY DRUG – STAGE 2	SAFETY POPULATION
TABLE 14.3.10.3	COMPLIANCE WITH STUDY DRUG – COMBINED STAGE 1 AND STAGE 2	SAFETY POPULATION

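### SAP 16.5 plans no IOP shift table, although Protocol Table 4-1 names IOP among the safety shift tables and SAP 18 declares no changes from the protocol

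*SAP*

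**What the plan says.** Protocol Table 4-1 sets out the endpoints for the primary objective. Its safety entries include "Shift tables for safety variables (e.g., IOP, biomicroscopy, and ophthalmoscopy"), and the Stage 2 row refers back to the Stage 1 list.

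SAP 16.4 and 16.6 plan shift tables for slit-lamp and fundus findings. SAP 20 carries them, beginning with "SHIFT IN SLIT-LAMP BIOMICROSCOPY – STAGE 1" and "SHIFT IN OPHTHALMOSCOPY – STAGE 1". For IOP, SAP 16.5 says that values and changes from baseline are "summarized using continuous descriptive statistics by visit and eye for each treatment group and for all actively treated subjects", and adds a subject listing. The matching entries in SAP 20 begin with "INTRAOCULAR PRESSURE (IOP; MMHG) – STAGE 1"; no shift title follows them.

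Two general statements govern the difference. SAP 1 says: "The statistical analysis methods presented in this document will supersede the statistical analysis methods described in the clinical protocol". SAP 18 says: "There are no changes from the protocol-stated analyses".

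**The concern.** Safety and tolerability against vehicle are the primary objective in both stages, and the protocol picked out IOP as one of three eye measures to be shown as shifts. A programmer working from the SAP would not produce that table, because the SAP takes precedence. A reader of SAP 18 would be told that nothing had changed.

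What is at stake is a count. IOP safety is usually judged by how many eyes rise by a clinically relevant amount, and a summary of means does not give that number. The adverse event tables give part of it, but they depend on the investigator judging a rise to be an event, and they do not report mmHg.

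**Working it through.** **Step 1: set the commitment beside the plan.** Counts are from SAP 20.

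| Variable named in Protocol Table 4-1 | SAP section | Summary tables | Shift tables |
|---|---|---|---|
| IOP | 16.5 | 3 (14.3.6.1 to .3) | 0 |
| Biomicroscopy | 16.4 | 3 (14.3.5.1.1 to .3) | 3 (14.3.5.2.1 to .3) |
| Ophthalmoscopy | 16.6 | 3 (14.3.7.1.1 to .3) | 3 (14.3.7.2.1 to .3) |

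One of the three named variables has no shift table, and SAP 18 does not record the omission.

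**Step 2: what the planned IOP tables can show.** SAP 8.4 defines continuous summaries as n, mean, SD, median, minimum and maximum. Take the largest Stage 1 active arm: 8 patients in Cohort 1 plus 45 in the expansion (Protocol 6.1) = 53 study eyes. The events are assumed: k eyes rise by 10 mmHg on top of background variation with mean zero.

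- Mean change = 10k/53. For k = 1 this is 0.19 mmHg; for k = 5 it is 0.94 mmHg. As shares of the arm, 1/53 = 1.9% and 5/53 = 9.4%.
- Maximum change: about 10 mmHg or more in both cases. The table shows that a large rise occurred.
- SD = sqrt(b² + 100·p(1−p)·53/52), with p = k/53 and b the background SD. For b = 2 to 3 mmHg (assumed), k = 1 gives 2.43 to 3.30 and k = 5 gives 3.56 to 4.21.
- The SD cannot be turned back into a count, because b is unknown. One eye with b = 3.3 gives sqrt(10.89 + 1.89) = 3.57, practically the same as five eyes with b = 2.0 (3.56).

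The presence of a large rise is visible; the number of eyes is not.

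**Step 3: which measurements enter.** The SAP 16.5 tables run by visit, and SAP 3.1 defines Visits 1 to 5. SAP 16.5 foresees IOP at an early-termination visit, and Protocol 10.4.2 allows it at unscheduled visits, but no rule says which row those readings feed. At the 10% dropout assumed for sample size, 0.10 × 53 = 5.3 and 0.10 × 47 = 4.7, so about 5 patients per Stage 1 arm could leave without a Visit 5 reading (47 = 2 + 45 on vehicle).

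**Step 4: what a largest-rise row would cost in interpretation.** Post-baseline IOP is scheduled three times (Visits 3, 4 and 5). With an assumed independent chance r of crossing a cut-off at each measurement, the ever-crossed rate is 1 − (1 − r)^m for m measurements.

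| r | m = 3 | m = 4 | Difference (points) | Effect on an arm if 10% have one extra (points) |
|---|---|---|---|---|
| 0.02 | 5.9% | 7.8% | 1.9 | 0.2 |
| 0.05 | 14.3% | 18.5% | 4.3 | 0.4 |
| 0.10 | 27.1% | 34.4% | 7.3 | 0.7 |

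Uneven unscheduled measurement could therefore create a small imbalance by itself. That is the reason to show the row both with and without those readings.

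**The case against.** The strongest defence is that the commitment is soft. Table 4-1 introduces the three variables with *e.g.*, Protocol 12.4.7 (the safety analysis section) does not repeat the shift tables, and Protocol 12 leaves detail to the SAP. IOP is continuous, and neither document gives IOP categories. SAP 1 also allows further analyses to be added and identified in the study report. This lowers the priority but does not remove the mismatch: IOP is named, and if it was dropped on purpose SAP 18 was the place to say so. Nor is a category table foreign to this SAP. For another set of continuous safety measures, SAP 16.8 states: "Vital signs will also be presented categorically for the number of subjects with low, normal, or high values".

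A reader might infer more than the documents support, in three ways.

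- *The IOP tables would hide a large rise.* They would not at a scheduled visit, because the maximum is reported by visit, eye and arm.
- *IOP safety information would be lost.* It would not. All data are listed (SAP 8.4), clinically relevant deterioration must be recorded as an adverse event (SAP 16.1), and the data review committee meets at least monthly (Protocol 13.7.6). Patients with glaucoma or ocular hypertension are excluded (Protocol 7.4).
- *The slit-lamp, visual acuity and fundus tables are in error because they do not show who ever worsened.* Neither document promises such a display, shift tables exist for slit-lamp and fundus, and visual acuity is not named in Table 4-1. Worst-value rows for slit-lamp and visual acuity, or a substitution rule for fundus exams, would be optional additions. A matched post-CAE slit-lamp comparison would also depart from the Visit 1 pre-CAE reference that SAP 16.4 specifies.

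**Conclusion.** The mismatch between Protocol Table 4-1, SAP 16.5 and SAP 18 is real and rests on the text alone. Its practical size is small: one of three named shift outputs is missing, and with it the number of eyes with a large IOP rise. No decision rule in the documents uses that number, and there is no expected direction of bias. The treatment of early-termination and unscheduled IOP readings is a missing detail that the same table can settle. The event counts, the 10 mmHg rise, the background SDs and the per-measurement rates are assumptions for illustration. Priority: minor.

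**What to change.** Add an IOP category or shift table, by arm and by eye, to SAP 16.5 and the 14.3.6 series.

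- Fix the cut-offs in advance, for example a rise of <5, 5 to <10 and ≥10 mmHg. The documents give none, so these are a proposal.
- Match baselines by time point as in SAP 8.3: Visits 3 and 4 against Day 1, and Visit 5 (post-CAE) against Visit 1 post-CAE. Compare off-schedule readings taken without CAE exposure with Day 1.
- Include one row for the largest post-baseline rise that counts early-termination and unscheduled readings, shown with and without the unscheduled ones.

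If the sponsor prefers not to produce the table, the least that is needed is to record its removal, with the reason, in SAP 18.

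The cost is SAP wording and one extra table for each of Stage 1, Stage 2 and the combined data, from measurements already collected. The drawback is that the largest-rise rate increases with the number of measurements in either arm, so it should be read beside the by-visit rows.
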